There is no documentation available showing the levodopa bioavailability for Duodopa vs. the i.v route. Based on the needed dosages of a levodopa solution administered i.v. to patients previously treated with Duodopa at the Linköping University Hospital, it may be estimated that Duodopa administered enterally is about 75% bioavailable as compared to i.v. administration. Experience from patients following s.c. administration at the same center suggests that equal doses of s.c. and Duodopa administrations can be used (Dizlin, data onfile). This suggested that the bioavailability of s.c. formulation may be in the range 75-100% when considering a complete dosage interval of a day. The dosage calculations for s.c. administration when starting the trial was hence based on the assumption of a 75% bioavailability. Analysis of data from the first 5 interim analysis patients, however, revealed that the absolute bioavailability of Infudopa s.c. is 100% vs. the i.v. standard, i.e. higher than expected (Clinical Study Interim Report 2019-01-15). Also Duodopa had a slightly higher absolute bioavailablity than the previous estimation (82% vs. i.v.). The ratio between LCIG and s.c. Infudopa levodopa bioavailability based on AUC 0-infinity was 0.78 and based on AUC 0-16 h 0.86. The AUC 0-16h was regarded as the most relevant variable for dose adjustment, because this is the time interval when the patient needs the optimal effect. Hence it was decided, that for the second part of the trial the dosage of Infudopa s.c. will be based on the assumption of an 86% bioavailability of Duodopa as compared to Infudopa s.c..

The aim of the present study will be to compare the pharmacokinetic and safety profile of Infudopa administered i.v. and s.c. with Duodopa administered enterally in patients with late stage Parkinson's disease.

## 1.4. Risk/Benefit evaluation

Patients with fluctuating Parkinson's disease, displaying on-off reactions to levodopa treatment, are usually severely disabled; this fairly common condition hence constitutes a major cause of poor life quality and is also, since these patients usually require intense care, associated with large societal costs. Any progress in this area should hence aid to meet a large unmet medical need.

The aim of this project, i.e. to facilitate the implementation of a novel treatment with the potential of markedly enhancing life quality and functioning of these patients within a foreseeable future, should not be regarded as overly optimistic. Thus, since

i) we already know that we are able to produce a concentrated solution of levodopa,

	Study code:	IPO-001
Clinical Study Protocol	Version No:	5.1
	Date:	26 MARCH
		2019

ii) we have good reasons to assume that s.c. administration of this solution will result in stable serum levels of levodopa, and

iii) previous studies regarding Duodopa have confirmed beyond doubt that producing stable serum levels of levodopa is indeed an effective way to improve motor functioning in patients displaying the on-off syndrome,

It is in fact not unlikely that s.c. Infudopa will turn out to be a major step forward with respect to the treatment of late stage Parkinson's disease. Moreover, albeit the decision of the authorities when assessing novel treatments for potential marketing may be difficult to predict, there are good reasons to believe that s.c. Infudopa, provided that the trial here presented is undertaken and successful, may reach patients in need within a relatively short future.

Also, as discussed above, today many patients with fluctuating Parkinson's disease are denied surgery such as orthopaedic surgery. The introduction of i.v. Infudopa for inpatients requiring a stabilisation of their motor functioning in order to cope with various forms of surgery (and the following rehabilitation), which might also be a consequence of this study, hence also must be regarded as an achievement of considerable clinical significance.

There is no reason to believe that Infudopa would exhibit any additional systemic adverse reactions than those described for other levodopa/carbidopa products, as summarised in the product information for Duodopa (see Investigator's Brochure). Duodenal administration of Duodopa has, however, a high risk of device- and procedure-related adverse reactions, such as postoperative wound infection, excessive granulation tissue, and incision site erythema, each reaction affecting more than 10% of patients (see Investigator's Brochure).

There is a potential risk of local adverse reactions at the administration site following Infudopa, however, local tolerance study in rabbits indicate that this risk should be low, and the reaction only short-term and not severe. However, the interim analysis of 5 patients showed that s.c. administration was associated with hematoma and transient and moderate pain or discomfort. Based on literature data, it was concluded that this was most likely due to the relatively high osmolarity caused by the high citrate concentration of the solution. Thus, when the trial starts again, a new buffer composition named Infudopa Buffer SubC, with a citrate concentration of only 20% of the previous one, will be used for the s.c. administration.

The half-life in plasma is short for levodopa, meaning that a lowering in pump rates following all routes of studied administration will quickly adjust down the levels of levodopa in plasma should, for example, dyskinesia occur. The clinical study is conducted at a phase I centre with intense monitoring of the patients that further reduces the risks. Please also refer to section 6.2 in the clinical study protocol for study dose and study design rationales. Data from the interim analysis have also given information allowing a fine tuning of the dosages.

When the study starts again, there will be a new interim analysis of pharmacokinetics (PK) and safety data after 4 of 18 (or 22 considering also possible compensatory patients) completed patients, after which a monitoring committee will meet to discuss the results and conclude if the study should continue, be modified with respect to design or discontinued. Evaluation will include blood PK samples, inspection of local dermal area/scoring including photos, and adverse events.

At high concentrations, citrate impairs coagulation. The levels of citrate (as well as those of phosphate) in Infudopa are, however, so low that no significant influence on systemic coagulation

Clinical Study Protocol		Study code:	IPO-001
	linical Study Protocol	Version No:	5.1
C		Date:	26 MARCH
			2019

even at maximal doses is to be expected, and also no other adverse effects of either citrate or phosphate. Nevertheless, safety laboratory analyses have been included in the study to monitor any possible effects on coagulation, by analysing total and ionized calcium and magnesium in serum, and blood base excess.

Hence, relevant precautions have been taken to minimize the risks and discomforts of patients participating in the study. This includes thorough information to the staff at the phase 1 unit where the trial will be conducted regarding the correct administration of the study product and the dose adjustments based on the clinical outcome (dyskinesia or on/off effect) that will aim to mitigate any adverse reactions.

In summary, it may be concluded that the risks for participating PD patients is low, and is outweighed by the profound benefit that a new s.c. and i.v. administration route would present to PD patients. Hence, the risk/benefit ratio for the clinical study is clearly beneficial.

## 2. STUDY OBJECTIVES AND ENDPOINTS

### 2.1. Primary objective

• To demonstrate that doseadjusted Infudopa s.c. yield steady state plasma concentrations of levodopa that are equivalent with those of Duodopa, that the variability in plasma concentrations during the dosage interval is non-inferior to that obtained with Duodopa., and to establish the absolute bioavailability of levodopa when given as Infudopa s.c. or Duodopa as compared to Infudopa i.v.

## 2.2. Secondary objectives

- To evaluate the safety of the products with special focus on the local tolerability at the injection sites of i.v. and s.c. administration
- To establish the bioavailability of carbidopa given s.c. and as Duodopa compared to the i.v. administration
- Compare other pharmacokinetic variables as well as motor function during treatment with s.c. and i.v. Infudopa versus Duodopa

## 3. STUDY DESIGN AND PROCEDURES

## 3.1. Overall study design and flow chart

This is a prospective, randomized, 3-period cross-over, open-label multicentre trial. Patients fulfilling all of the inclusion and none of the exclusion criteria will be randomized to one of the three treatment arms. There have been 5 interim patients already studied. Enrolment upon restart of the study will be continued until the required sample size is achieved (18 subjects in total entering the second part of the study, giving in total 23 subjects in the study). Once informed consent is

[figure not shown]
	Study code:	IPO-001
Clinical Study Protocol	Version No:	5.1
	Date:	26 MARCH 2019

obtained, screening data will be collected to determine each patient's eligibility for study participation.

The duration of subject participation in the study is expected to be around 3-4 months from screening to final follow-up (with variation depending on subject's availability between treatment visits), and the subject will be on study treatment for in total 3 days.

Patients with Parkinson's disease who are on Duodopa treatment because of severe on- off manifestation when on oral levodopa will be identified and recruited by experienced neurologists at neurology clinics at university hospital clinical sites in Sweden. Patients will travel from their living location to a clinical phase I site with full Good Clinical Practice (GCP) standard at the Sahlgrenska University Hospital in Gothenburg for the three treatment visits.

The subjects will be assessed at the phase I study clinic, where they during one treatment visit will receive Duodopa at optimal dosage for 16 hours, during another treatment visit will receive i.v. Infudopa at a concentration estimated to yield corresponding serum levels of levodopa for the same duration, and at a third treatment visit will again receive the corresponding amount of levodopa but in the form of s.c. Infudopa. The study will hence have a cross-over design with a minimum of three days on Duodopa between the different treatment visits, where the order of treatments will be non-blinded but randomized.

#### Figure 1 Study design

#### 3.2. Study visits

Table 1 lists all of the assessments and indicates with an "X" the visits when they are performed. Table 2 lists the assessments during the treatment visits in more detail. All the obtained data must be supported in the subject's medical records (or equivalent), i.e. source documentation.

	Study code:	IPO-001
Clinical Study Protocol	Version No:	5.1
	Date:	26 MARCH 2019

Subjects who for any reason discontinue study drug before completing the study should be scheduled for an End-of-Study visit as soon as possible, at which time all of the assessments listed for the End-of-Study visit will be performed.

Procedure	Scree- ning		eatme Visit 1		Return to Duodopa 1		eatme Visit 2		Return to Duodopa 2			Treatment Visit 3		Infudopa s.c. Follow- Up Visit	End-of-Study Visit
Day within study period	-60 to -2	-1	1	2	3 days minimum	-1	1	2	3 days minimum	-1	1	2	3-5	30 days after Infudopa s.c. Day 2 (+/- 5 days)	30 days after V4, Day 2  (+/- 5 days)
Visit	1			2				3				4		F-U 	5
In house confine- ment		х	х	х		х	x	x		х	x	х			
Informed consent	х														
Demography & Medical History	х														
Physical examination	х														х
12-lead ECG	х														
Vital signs	х	х	х			х	х			х	х				х
Height, weight	х														
Previous / concomitant treatment	х	х				х				х					Х
Use of per protocol drugs during levodopa nighttime withdrawal		Х	Х	X		X	X	X		Х	x	Х			
Pregnancy test (for females)	х	x				x				х					
Laboratory	X9		х	х			х	х			х	х			х

Study code:	IPO-001
Version No:	5.1
Date:	26 MARCH
	2019

In-/exclusion criteria	x	x				X1				X1					
Randomi- zation		x													
Treatments			х				х				х				
Inspection of local dermal area/scoring		x	х	х		х	х	х		х	х	х		х	Х
Photo of local dermal area		X 		x		X4		х		X4		х		X 	X 
Blood PK samples⁵			х	х			х	х			х	х			
Adverse Events	X6	х	х	х	X7	х	х	х	X7	х	х	х	X7	х	х
Study completion form															х
Efficacy measure- ments (video, PKG)			х	X 			х	X 			x	X 			

 At the discretion of the Investigator, the subjects could continue the study if any deviation to the inclusion/exclusion criteria is not clinically relevant and should not alter study integrity.

Infudopa s.c. follow-up visit should be performed 30 days after the end of the Infudopa s.c. treatment visit. It can be done as part of the End-of-Study visit if applicable, otherwise as a separate visit at the local site.

End-of-Study visit should be performed as soon as possible if the subject is prematurely withdrawn from the study.

Photo will always be taken at day -1 and day 2 of each treatment visit, but only to document any abnormalities at the Infudopa s.c. follow-up visit and the End-of-Study visit.

See Section Study Procedures, Drug levels and pharmacokinetic assessments, for schedule of blood collection.

SAEs must be collected from time of informed consent. AEs from time of study drug administration.

Phone call on Day 3 and 5 (acceptable to adjust for week end and call the next week day if applicable) after treatment visit 1, 2, and 3, respectively.

PKG up to morning of Day 2

Prothrombin complex (PTK-INR), Activated Partial Thromoplasmin Time (APTT), HIV and Hepatit B and C only applicable at the screening visit

### Table 2. Assessment schedule, Treatment Visits

Day within visit	-1											1													2		
Time point (h)	after noon	Pre dose	0	15 min	30 min	1	1,5	2	2,5	3	3,5	4	5	6	7	8	9	10	12	14	16	16,5	17	17,5	18	23	24
Vital Signs	х	х																									
Pregnancy Test (for females)	х																										
Randomization 	x																										
In-/exclusion criteria 	x																										 
Previous / concomitant treatment	x																										
Use of per protocol drugs for levodopa abstinence	х	х																			х	х	х	х	х	х	х
Treatment			х	х	х	х	х	х	х	х	х	х	х	х	х	х	х	х	х	х	х						
Inspection of local dermal area/scoring	х							х								х					х						х
Photo of local dermal area	х																										х
Food 							х					х				х			х								х
Adverse Events 	х	х	х	х	х	х	х	х	х	х	х	х	х	х	х	х	х	х	х	х	х	х	х	х	х	х	X5
Video recording 		х					х						х	х	х					X6							
PKG		х	х	х	х	х	х	х	х	х	х	х	х	х	х	х	х	х	х	х	х	х	х	х	х	х	х
Blood PK samples 			х	х	х	х	х	х	х	х	х	x	х	х	х	х		х	х	х	х	х	х	x	х	x	х
Laboratory Tests 																											X 

**Clinical Study Protocol** 

Study code:	IPO-001
Version No:	5.1
Date:	26 MARCH 2019
	2013

|--|

Randomization, only at Treatment Visit 1

At the discretion of the Investigator, at treatment visit 2 and 3, the subjects could continue the study if any deviation to the inclusion/exclusion criteria is not clinically relevant and should not alter study integrity.

Adverse Events collected throughout the study as described in section 7.

Including question at day 2 about subject's experience during the treatment day.

Starting 15 (±5) min after the blood PK sampling. Assessment at 14 h can be omitted for practical reasons (exact reason documented in the eCRF).

Laboratory tests on Day 2 only at the third Treatment Visit (according to Table 1).

Low-protein snack is allowed between meals if needed

PK sampling should be prioritised at time points when more than one procedure is scheduled at the same time point

This time point samples only for total and ionized calcium and magnesium in serum, and blood base excess.

#### Visit 1, Screening visit (day -60 to -2):

The subject will receive information about the study. After the informed consent document has been dated and signed, both by the subject and the investigator, and the subject has been provided with a copy of the subject information and a copy of the signed informed consent form, screening information will be obtained.

The subject will be allocated a unique subject number.

The procedures to be undertaken are shown in Table 1, and results entered into the electronic Case Report Form (eCRF).

The visit will take approximately 90 minutes.

#### Visit 2, 3 and 4, (day -1 to 2 in each treatment visit)

Within 60 days after the screening visit, eligible subjects fulfilling all inclusion criteria and none of the exclusion criteria will be asked to come to the phase I unit in Gothenburg for the first treatment visit on Day -1 of treatment visit 1. It will be adequate for subjects to arrive at the phase I unit in the afternoon for procedures according to Day -1 of treatment visit 1. Randomization of subjects will be made on Day -1 of treatment visit 1.

At Day -1 in treatment visit 2 and 3 subjects will also be admitted to the clinical site. The procedures to be undertaken are shown in Table 1 and 2.

No Duodopa or oral levodopa–carbidopa or levodopa-benserazide tablets will be allowed later than 7 h prior to the start of the infusion on the day of pharmacokinetic assessments (i.e. last dose approximately 23.00 the night before).

Prior to the pharmacokinetic sampling, subjects will be fasted overnight (starting from 22:00 on the previous day). On the pharmacokinetic assessment day, subjects will receive the same standardized, low protein meals at the following approximate times relative to starting infusion: breakfast (1.5 h, +/-15 min), lunch (4 h, +/-30 min), dinner (8 h, +/- 30 min), and evening meal (12 h, +/- 30 min). Water will be allowed ad libitum. After the end of blood sampling, before leaving the clinic, they will be served breakfast.

At day 1 of the treatment visits, drug administration will start early in the morning and continue for 16h. Whole blood samples will be collected via an indwelling catheter or by direct venous puncture during the visit immediately prior to the initiation of treatment in the morning and at the following time points after the initiation of infusion (0h):

PK sample	Time window for sampling
Pre-administration	- 30 to 0 min
15 min	+/- 1 min
30 min	+/-1 min
1 h	+/- 5 min
1.5 h	+/- 5 min
2 h	+/- 5 min
2.5 h	+/- 5 min

#### Table 3. PK sampling details

3 h	+/- 5 min
3.5 h	+/- 5 min
4 h	+/- 5 min
5 h	+/- 10 min
6 h	+/- 10 min
7 h	+/- 10 min
8 h	+/- 10 min
10 h	+/- 10 min
12 h	+/- 10 min
14 h	+/- 10 min
16 h	+/- 10 min
16,5 h	+/- 10 min
17 h	+/- 10 min
17,5 h	+/- 10 min
18 h	+/- 10 min
23 h	+/- 15 min
24 h (for patients on	+/- 15 min
Duodopa treatment, the PEG	
tube should be flushed at 24	
h, after the PK sample has	
been taken)	

A video recording of the subject will be made for subsequent assessment of motor function. During Day 1, subjects will be video recorded for 1 to 2 minutes pre-dose and after start of medication according to Table 2. The video recordings will be made just after any blood sampling. The video sequences will subsequently be assessed by two blinded, independent neurologists as secondary efficacy variable (see 3.3.8 Video Recordings). Blinding of the assessing neurologists will be obtained by having the subjects equipped with dummy infusion lines, so that the actual treatment arm could not be judged from the video sequences.

Moreover, a Parkinson's KinetiGraph (PKG; Global Kinetics Corporation, Melbourne, Australia) for collection of efficacy data (Griffiths et al, 2012) will be used. The PKG automatically collects accelerometry data from spontaneous wrist movements and scores the degree of bradykinesia and dyskinesia as well as detects tremor (see 3.3.9 Parkinson's KinetiGraph).

Adverse event monitoring and inspection of local dermal area including scoring will be undertaken as shown in Table 1 and 2. The local tolerability will be assessed and photographs subsequently evaluated by a dermatologist (see 3.3.6 Inspection of local dermal area/scoring including photos).

Subjects will leave the clinical site in the morning on Day 2 after initiating their standard treatment and having breakfast.

#### Return to Duodopa treatment between Visit 2-3 and Visit 3-4

It is required that the subjects return to Duodopa treatment for a period of minimum 3 days between Treatment Visit 2 and Treatment Visit 3, and between Treatment Visit 3 and Treatment Visit 4, respectively.

There will be telephone follow-ups of the subject from the site in Gothenburg on the day after (Day 3) and 3 days after (Day 5) treatment visit 1, 2 and 3, and, if needed, a visit at the local clinic for follow-up if there are possible adverse events that have to be assessed/followed up during these periods. If needed, additional telephone follow-ups will be made.

### Infudopa s.c Follow-Up visit

Approximately 30 days (+/- 5 days) after the end of the treatment visit where the subject was randomized to receive Infudopa s.c., the subject will visit the local Investigator for a follow-up inspection of the local dermal area. The visit will include an inspection of local dermal area/scoring, with photos if anything abnormal is identified.

This visit can be done at the same time as the End-of-Study visit, or be combined with a treatment visit if applicable, but will otherwise be performed as an individual visit 30 days after the s.c. treatment.

### End-of-Study visit, Visit 5

An End-of-Study visit will be performed by the local Investigator approximately 30 days after the end of the third treatment visit (Table 1). If a subject is prematurely withdrawn from the study, an End-of-Study visit will be performed as soon as possible following the decision to withdraw. The visit will include an inspection of local dermal area/scoring, with photos if anything abnormal is identified.

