#### 3.3.7. Inspection of local dermal area/scoring including photos

Inspection of local dermal area, including adverse event scoring, and photos will be performed at the site in Gothenburg at day -1 and day 2 during the treatment visits. The same assessments will be made at the Infudopa s.c. follow-up visit and the End-of-Study visit by the local Investigator. In addition to visual inspection and photo documentation of the skin area the area will be assessed for increased subcutaneous consistency, tenderness and pruritus (itching). Pain, tenderness and itching, respectively, will be rated by the subject using a horizontal 10 cm visual analogue scale (VAS) (Furue et al, 2013 and Younger et al, 2009). In the event of any occurrence of noduli or increased subcutaneous consistency, it will be photographed, and then the approximate borders will be delineated on the skin with a pen and photographed.

Photos will always be taken at day -1 and day 2 of each treatment visit according to provided instructions, and to document any abnormalities at the Infudopa s.c. follow-up visit, and at the End-of-Study visit. Photos of the skin area will be taken using a dark background behind the subject.

Perpendicular artificial lighting will be used and the subject will be asked to relax muscles. The subject will be photographed in dorsal recumbent position on all occasions. A 10 cm paper ruler tag will be placed at on the skin at the side of the infusion site and the full length of the ruler included in view. The subjects face or other identifiable features will not be included.

The photos will be assessed and scored according to the Draize Score (refer to Appendix B) by two blinded and independent dermatologists, and photos will be randomized between time, subjects and treatments for the assessment. The assessors will be trained before the study, and the order of the photos will be broken when all assessments are finalized. Estimation of area of the affected skin will be made, using the above-mentioned ruler as a calibration unit.

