Adverse events involving the skin will be evaluated by study personnel when prompted by the subject and at the pre-defined time points. At the pre-defined time points any occurrence of the following pre-defined symptoms will be assessed and severity rated: erythema, discoloration, pain, pruritus, subcutaneous nodulus or tenderness. Predefined infusion related **adverse events** involving the infusion sites are: Acute transient infusion site reaction, Continuous infusion site reaction and delayed infusion site reaction which when appropriate can be described with other terms listed under the class "General disorders and administration site conditions" - "Infusion site reactions" or "General disorders and administration site conditions" - "Implant and catheter site reactions" See:

http://bioportal.bioontology.org/ontologies/MEDDRA/?p=classes&conceptid=http%3A%2F%2Fpurl. bioontology.org%2Fontology%2FMEDDRA%2F10018065. When appropriate, free text terms can be used.

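### Blinded skin scores at the s.c. follow-up and End-of-Study visits exist only where the open-label local investigator has already seen an abnormality

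*Protocol*

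**What the plan says.** Section 3.2 (Table 1 and its footnotes) and section 3.3.7 set two photo rules. On day -1 and day 2 of every treatment visit a photo is always taken. At the Infudopa s.c. follow-up visit and the End-of-Study visit photos are taken "only to document any abnormalities at the Infudopa s.c. follow-up visit and the End-of-Study visit". The visit descriptions in 3.2 repeat this restriction for both visits, where the assessor is the local investigator.

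Under 3.3.7 the photos are scored on the Draize scale (Appendix B) by two dermatologists who do not know the treatment, and "photos will be randomized between time, subjects and treatments for the assessment". Section 8.2 then summarises local tolerability descriptively by visit and as change from baseline. Among the predefined skin events, 3.3.7 lists "Continuous infusion site reaction and delayed infusion site reaction".

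On visit timing, 3.2 ties the s.c. check to the s.c. infusion: "Approximately 30 days (+/- 5 days) after the end of the treatment visit where the subject was randomized to receive Infudopa s.c., the subject" is to see the local investigator for a skin inspection. Table 1 footnote 2 adds: "It can be done as part of the End-of-Study visit if applicable, otherwise as a separate visit at the local site". For patients who stop early, 3.2 says: "Subjects who for any reason discontinue study drug before completing the study should be scheduled for an End-of-Study visit as soon as possible". Its description of the End-of-Study visit repeats that, after premature withdrawal, "an End-of-Study visit will be performed as soon as possible following the decision to withdraw".

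**The concern.** The trial is open-label, so the blinded photo reading is the one local tolerability measure protected from knowledge of treatment. At the follow-up visits that protection is lost at the point of entry. An unblinded assessor first decides whether the skin is abnormal, and only then does a photo exist for the blinded readers.

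This matters because local tolerability is the focus of the first secondary objective (2.2), and section 1.2 promises to monitor it both on the ward and at follow-up. It is also the reason the s.c. buffer was reformulated after the first five patients (1.4). A reader of the final report will want a blinded statement that the skin was clear, or had healed, about a month after the new s.c. formulation. As written, the blinded reading cannot supply one.

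**Working it through.** No sample size, power or error rate is involved. The check sets the provisions side by side, with small arithmetic for scale.

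**1. Which photos after s.c. are assured** (Tables 1 and 2, footnote 4, 3.3.7)

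| s.c. given in | Assured photos after s.c. | Photos only if abnormal |
|---|---|---|
| Treatment visit 1 | Day 2; then day -1 and day 2 of treatment visits 2 and 3 | s.c. follow-up, End-of-Study |
| Treatment visit 2 | Day 2; then day -1 and day 2 of treatment visit 3 | s.c. follow-up, End-of-Study |
| Treatment visit 3 | Day 2 only | s.c. follow-up and End-of-Study, which share the same target day |

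- Table 2 puts the day 2 photo at 24 h. Infusion stops at 16 h, so it is taken 24 - 16 = 8 h after infusion ends.
- The gap between treatment visits is at least 3 days (3.2), so the next day -1 photo may come only days after s.c.
- Assuming each treatment is equally often last, 18/3 = 6 patients in the second part receive s.c. last.
- A patient who leaves after s.c. and before the next treatment visit is in the same position.

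**2. What the conditional score can show at follow-up**

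- Skin normal throughout: no photo, so no blinded confirmation.
- Reaction on day 2, healed by follow-up: no abnormality, no photo, so no blinded record of healing.
- Reaction persisting: photo and score.
- Slight reaction not noticed locally: no photo, so the blinded readers cannot pick it up. Appendix B gives grade 1 to erythema or oedema that can only just be seen.

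Only the third case produces a score. Change from baseline at these visits can be calculated from photos only in patients called abnormal.

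**3. Effect on a summary (assumed figures, for illustration only)**

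Let n patients attend, k be called abnormal, and m be the mean Draize score among those k. The mean over available photos is m. The mean over all n, if the others would have read zero, is k x m / n. With n = 18 and m = 2:

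- k = 2: 2 x 2/18 = 0.22, against 2.0 from available photos
- k = 4: 4 x 2/18 = 0.44, against 2.0
- k = 9: 9 x 2/18 = 1.00, against 2.0

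The protocol gives no values for k or m and does not fix how unphotographed visits are counted.

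**4. Withdrawal**

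- Table 1 footnote 3 moves one visit only: "End-of-Study visit should be performed as soon as possible if the subject is prematurely withdrawn from the study".
- The s.c. follow-up has its own column in Table 1 and its own timing. If it is not merged with another visit, 3.2 has it done as an individual visit at 30 days.
- Footnote 2 allows merging with the End-of-Study visit without saying that this visit must then fall 25 to 35 days after s.c.
- Section 4.5 names only serious adverse events for follow-up after discontinuation.

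No sentence says that the early visit replaces the skin check, and none says that a withdrawn patient keeps it. For scale, 8.1 allows 4 drop-outs in 22 (4/22 = 18%), from any cause. With balanced order and withdrawal unrelated to treatment, one third of those leaving after one treatment visit and two thirds of those leaving after two would have had s.c.: 4 x 1/3 = 1.3 to 4 x 2/3 = 2.7 patients. If s.c. itself prompted every withdrawal, it would be all 4.

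**The case against.** The strongest reply is that photos are documentation and not the means of detection. At both follow-up visits the skin is inspected and scored in every attending patient, subcutaneous consistency is assessed, and pain, tenderness and itching are rated on a VAS (3.3.7). Adverse events are collected at both visits (Table 1). Nodules are found by palpation, and the Draize scale has no item for them. This stands. A reader might infer that delayed s.c. reactions are selectively missed, or that the tolerability result for the new buffer is biased. The documents do not support either, because none of these assessments depends on an abnormality being seen first.

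A reader might also infer that a withdrawn patient gets the early End-of-Study visit in place of the 30-day skin check. The text does not say so: the check is a separate visit, and only the End-of-Study visit is brought forward. Nor is follow-up shown to be shortest in those who reacted. Section 7.2.1 requires supervised care until symptoms cease or stabilise after removal or withdrawal for an adverse event, and 7.2.2 follows related events to resolution or stability. Calls on days 3 and 5 add to this. What remains is silence about a non-serious reaction that first appears after an early End-of-Study visit.

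Patients who continue after s.c. in the first or second treatment visit do get a later unconditional day -1 photo. That narrows the point but does not remove it. It does not help when s.c. is last, and the protocol does not state that the photo covers the earlier s.c. site.

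Finally, the handling of unphotographed visits may be left to a SAP. That is fair for the averaging rule, but no analysis rule can recover a blinded reading of a photo never taken. Entering zero would put the open-label judgement into the blinded score.

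**Conclusion.** The point holds for the blinded photo score at the s.c. follow-up and End-of-Study visits. That score is available only for skin the open-label local investigator has already judged abnormal, so it cannot confirm normal or healed skin or audit the local judgement, and its by-visit and change-from-baseline summaries are selective. It matters most for patients who receive s.c. last: about 6 of 18 if order is balanced, with no assured photo later than about 8 h after the infusion. The numerical effect on a summary cannot be known from the protocol; the figures shown rest on assumed counts and scores.

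It is a worthwhile low-cost improvement to a secondary safety measure. It does not show that reactions go undetected. The withdrawal question is secondary: an ambiguity touching perhaps 1 to 3 patients, at most 4, under the stated drop-out allowance.

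**What to change.** Change Table 1 footnote 4, the two follow-up visit descriptions in 3.2, and 3.3.7 so that the standard photo is taken in every attending patient at the s.c. follow-up and End-of-Study visits. For the s.c. question it should include the s.c. infusion area. State that all these photos enter the randomised blinded reading. The cost is some additional images for readers already engaged, at visits already held.

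Separately, reconcile the text of 3.2 with Table 1 footnotes 2 and 3. State whether a withdrawn patient who received Infudopa s.c. keeps the separate 30 (+/- 5) day skin check, and whether merging it with the End-of-Study visit is limited to that window. The clarification costs a sentence or two. If the check is kept, it adds at most a local visit for the few withdrawn patients willing to attend.
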